7.2. Methods and measurement times

- Reference Ulcer area, volume and perimeter measurements:

The 3D pictures of RU will be taken and uploaded to a secured website at each visit after wound cleansing by the investigator (or a delegated person) (except at the selection visit with two pictures: one before cleansing and debridement and another one after cleansing and debridement).

The RU area will be measured by the investigator at selection by tracing the RU outlines using a transparent sheet after wound cleansing and debridement. In addition, two 3D pictures will be taken and uploaded by the investigator (or a delegated person) at the ASSE visit for the central measurement by the CRO for the efficacy analysis. The CRO will send the two pictures to the independent expert with an alert system. The central measurement of RU area will be sent back to the investigator and if the central measurement is not fitting the selection criteria, the participant will be withdrawn before inclusion.

Three (or four) working days before inclusion visit (W000), the participants will come to the site for a RU picture. The investigator (or a delegated person) will upload the image on a secured website on the same day. The CRO in charge of the central reading will receive the picture, perform RU area measurement, and send it back to the investigator within the three following working days and before the inclusion visit.

The CRO will also send to the investigator the central RU area measured on the picture taken 3 (or 4) working days before W000 and the calculation of the change between ASSE and W000 area measurements.

At selection, an independent expert will check the feature of RU. The expert will give an opinion on the RU by reviewing the clinical aspect of RU on the 3D pictures. The expert will confirm the selection or not if RU clinical pictures are consistent with a venous aetiology or give a recommendation for study continuation. If a doubt exists on the venous aetiology of the RU, another expert will give a second opinion on the picture. If the doubt of the venous origin of the RU persists, the expert in charge of the review of the picture at selection will review the picture taken at inclusion. If the doubt still persists at the review of the picture taken at inclusion, the patient will not be included.

At the inclusion visit (W000), these measurements will be used by the investigator to check if the RU area was in the range of inclusion criteria and if the change in the RU area between ASSE and W000 is less or equal to 20% for inclusion.

Area Change $w_0-ASSE = | \text{Reference Ulcer Area W000} - \text{Reference Ulcer Area ASSE} | / \text{RU Area ASSE}$. (Reference Ulcer Area ASSE is the one after cleansing and debridement).

Patients found to be eligible for randomisation will also have a 3D picture of the RU on the day of W000 (taken after randomisation) that will be uploaded by the investigator (or a delegated person) on the secured website to send these pictures to the central reviewer.

At W001, W002, W003, W004, W006 and W008, the investigator (or a delegated person) will upload the 3D pictures of RU on the secured website to send these pictures to the central reviewer.

In addition to the RU area measurement, the CRO in charge of the central measurement will perform volume and perimeter measurements at each visit on the 3D picture. These measures will be used for the efficacy criteria.

- Pain assessment

The questionnaire with the VAS will be provided by I.R.I.S and completed at the beginning of W000, W004 and W006 visits, before RU clinical assessment and local care of the RU. The participant will draw a vertical line on the scale to reflect his perception on the intensity of the pain since the last visit. The investigator will measure the exact distance from 0 to the line

drawn by the participant and report the corresponding measurement in millimetres in the e-CRF together with documenting the answers to all the questions.

- Reference Ulcer clinical assessment

The form for RU clinical assessment will be completed after the pain assessment and will be reported in the e-CRF at each study visit: ASSE, W000, W001, W002, W003, W004, W006 and W008.

- Analgesic drug consumption:

Analgesic intake follow-up related to VLU: will be evaluated and reported in the e-CRF at W000, W004 and W006 visits and will be addressed to patient using analgesic drug linked to VLU.

8. SAFETY MEASUREMENTS

8.1. Safety measurements

Safety measurements performed during the study are indicated in [Table \(4.2.2\) 1](#).

- Recording of any adverse event occurring during the study using the collection methods detailed in [section 8.3](#).
- Physical examination, body weight measurement, vital signs, 6 or 12-lead electrocardiogram (ECG), standard urinalysis and laboratory assessments.

8.2. Methods and measurement times

- Physical examination

Physical examination will be a clinical exam carried out by the investigator at all visits in order to assess participant's condition before deciding to keep the participant in the study. The abnormalities of the physical examination will be reported and evaluated by the physician as clinically significant or not. Any clinically significant changes during the study should be recorded as an adverse event.

- Weight

The participant's weight will be determined at selection (ASSE), inclusion (W000), W002, W006 and W008. It should be measured under the same conditions (i.e. same scale, empty bladder, before breakfast, being only lightly dressed).

The participant's height will be measured at the selection visit for participant's BMI calculation.

- Vital signs

Blood pressure and heart rate will be measured at all visits, they should always be measured under the same conditions for each participant during the study (one measure after 10 minutes in the sitting position). Body temperature will be recorded at all visits for on-site safety.

- Standard electrocardiogram

A standard electrocardiogram ECG (6 or 12-lead) will be performed within the 5 calendar days prior to W000 visit, with results available at W000 visit (at the latest) before randomisation, to check that there are no clinically significant abnormalities. If the investigator does not have the expertise to read ECG tracings and/or in case of abnormalities, the ECG should be verified by a cardiologist prior to the inclusion of the participant in the

study. The ECG will be performed after 15 minutes at rest with the participant in supine position. It will be recorded at speed 50 mm/s with 2 cm/mV amplification and with at least 3 QRS complexes by lead.

The 6 or 12-lead ECG will be repeated at all subsequent visits. If the investigator does not have the expertise to read ECG tracings and/or in case of abnormalities, the ECGs should be verified by a cardiologist. Any clinically significant abnormality discovered must be recorded as an adverse event in the e-CRF. The following parameters are to be recorded: rhythm, heart rate, PR interval, QRS duration, QTc duration and RR interval [QTc calculated using Fridericia formula (QTcF = QT / $\sqrt[3]{RR}$)]

In order to avoid the possible artefacts in the ECG interpretation (e.g. hysteresis effect in which an increase in HR is followed more slowly by an adaptation of QT duration and consequently lead to an alteration of QT-RR relationship), it is recommended to follow the below recommendations:

- To allow the subject to be reclining at rest for at least 15 minutes prior to ECG acquisition and in this time no emotional stimulation of the subject is allowed (TV, vital sign acquisition, blood sampling) as they might have an impact on heart rate.
- To perform blood sampling after the ECG recording when the same time points are needed for blood sampling and ECG acquisition.

- Laboratory assessments

Local laboratories will be responsible for analysing the biochemistry and haematology samples, FSH, β -HCG. The laboratory will send a laboratory report to the investigator who will be responsible for the clinical assessment of the results and data entry in the e-CRF. Any clinically significant abnormal laboratory value should be recorded as an adverse event in the e-CRF. The investigator should follow up all clinically relevant changes until recovery.

- Biochemistry (within the 5 calendar days prior to W000 with results available at W000 at the latest, W001, W002, W004, W006 and W008 visits): AST (SGOT), ALT (SGPT), CPK, alkaline phosphatase, GGT, total bilirubin, total protein, albumin, Calcium, Urea, Creatinine, CRP, glucose, Na, K and Cl. The analyses will be done under fasting condition (10 hours). Within the 5 calendar days prior to W000 with results available at W000 at the latest, a test for HbA1c must be done for all patients except known diabetics with a result \leq 8% obtained in the 3 months before the selection visit.
- Fasting Lipids (within the 5 calendar days prior to W000 with results available at W000 at the latest, W001, W002, W004, W006 and W008 visits): Triglycerides, HDL, LDL, and total cholesterol. The analysis will be done under fasting condition (10 hours).
- Haematology (within the 5 calendar days prior to W000 with results available at W000 at the latest, W001, W002, W004, W006 and W008 visits): haemoglobin, haematocrit, red blood cells, MCV, MCH, MCHC, platelets, white blood cells, lymphocytes, monocytes, eosinophils, basophils and neutrophils (white blood cells, lymphocytes, monocytes, eosinophils, basophils and neutrophils must be assayed in absolute value and entered in the e-CRF in this unit). For patients under warfarin or phenprocoumon, International Normalized Ratio (INR) will be performed at each visit (including W003) or more often if judged necessary by the investigator.

- Standard urinalysis will be performed using a dipstick, within the 5 calendar days prior to W000 with results available at W000 at the latest, W004, W006 and W008 visits by the investigator or a delegated person. Urinalysis: pH, proteins, blood, leucocytes, bilirubin, ketones bodies, nitrites and glucose.
- A blood sampling will be performed for β -HCG or FSH analysis (within the 5 calendar days prior to W000 visit, with results available at W000 visit at the latest) to diagnose pregnancy and menopause respectively. β -HCG tests will be repeated at W004 and W008 visits for women of child-bearing potential. Depending on the local regulation, pregnancy tests can be additionally repeated throughout the treatment period (urinary tests which is not to be entered into e-CRF).

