The parameters of the selected model in the main analysis will be re-assessed and, if the model converges, it will be used to estimate the MED. If the model doesn’t converge, the second “best” fit model will be used.

- Description

The relative change from baseline of the reference ulcer area will also be described at each visit.

- Secondary criteria

- Linear advance of the wound margin towards the wound centre

Description at each visit will be provided.

- Reference Ulcer Volume

Descriptive statistics at each visit will be performed.

- Pain intensity

Descriptive statistics at each visit will be carried out.

- Analgesic drug consumption

Descriptive statistics at each visit will be carried out.

In addition, relative change of the reference ulcer area, linear advance of the wound margin towards the wound centre and reference ulcer volume will be described at each visit in the following subgroups:

- Combined prognosis criteria on size and age of the ulcer ($\leq 10 \text{ cm}^2$ and ≤ 6 months / $> 10 \text{ cm}^2$ or > 6 months)
- Size of the ulcer at baseline ($\leq 50 \text{ cm}^2$ / $> 50 \text{ cm}^2$)
- Diabetes status (yes/no).

Exploratory data analyses will be conducted as applicable.

Safety

Safety analyses will be carried out on the Safety Set by group over the W0-W6 period.

- Adverse events

Number of adverse events, number and percentage of patients reporting at least one adverse event will be described by System Organ Class (SOC) and Preferred Term. The same analysis will be performed for emergent adverse events and serious adverse events.

Emergent adverse events will be also described in accordance to the intensity, outcome, relationship to the study treatments, and adverse events leading to the study drug withdrawal.

- Clinical laboratory evaluation

Laboratory parameters will be described using value at the visit, last value under treatment and change from baseline to last value under treatment.

Moreover, biochemistry, haematology and urinary parameters will be classified according to the laboratory reference ranges and alert values for the potentially clinically significant abnormal values, and shift tables from baseline to worst event will be presented.

- Physical Examination and vital signs

Physical examination and vital signs will be described using value at the visit, last post-baseline value and change between baseline and last post-baseline value.

- 6 or 12-lead electrocardiogram (ECG)

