3.6.2. Clinical laboratory evaluation

For all parameters, the **dosing of samples come from local laboratories**. So no quantitative analysis will be performed. In the qualitative analysis, data will be compared to reference ranges provided by these local laboratories.

Definition:

- A laboratory value is considered as analysable if non-missing and not flagged in the ClinTrial database as "not analysable".

Analyses:

For each biochemical and haematological parameter, the following analyses will be performed:

- Number and percentage of patients with at least one high/low emergent abnormal value under treatment, according to the laboratory reference ranges and to the cut-offs for PCSA values.

- Laboratory parameters classified (number and percentage of patients in each class) according to these reference ranges and cut-offs, and using shift tables from baseline to the worst (high and/or low) values under treatment.

Moreover, listings of patients with out-of-range or PCSA analysable values emergent under treatment and of non-analysable values excluded from analyses will be provided.

Urinary parameters will be described in classes (absent, trace, +, ++, +++, +++) at baseline and at each post-baseline visit under treatment.

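### SAP 3.6.2 leaves urinalysis out of the baseline-to-worst shift tables that protocol 10.1.4 plans, and the SAP's table of main changes does not say so (minor)

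*Protocol*

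**What the plan says.** Protocol 8.2 schedules a site-read dipstick ("Standard urinalysis will be performed using a dipstick, within the 5 calendar days prior to W000", then at W004, W006 and W008) with eight items: "Urinalysis: pH, proteins, blood, leucocytes, bilirubin, ketones bodies, nitrites and glucose". Standard urinalysis is named in the secondary objective on the safety profile of each tested dose (protocol 3.2, SAP 1.1).

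Protocol 10.1.4, under clinical laboratory evaluation, says that "biochemistry, haematology and urinary parameters will be classified according to the laboratory reference ranges and alert values" for potentially clinically significant values. The same sentence ends by stating that "shift tables from baseline to worst event will be presented". Urine is therefore inside the shift-table commitment.

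SAP 3.6.2 opens its two analysis bullets with "For each biochemical and haematological parameter, the following analyses will be performed". The bullets are the count of patients with an emergent high or low value, and the classification "using shift tables from baseline to the worst (high and/or low) values under treatment". Urine has one separate sentence: "Urinary parameters will be described in classes", at baseline and at each post-baseline visit under treatment. SAP 3.6 has all safety analyses presented by treatment group.

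The follow-up-of-versions table at the front of the SAP sets out the main changes from the protocol analyses. It includes an item as small as dropping heart rate from the ECG description. It has no entry for urinalysis.

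**The concern.** A class distribution at each visit is a marginal count. It does not tie a patient's result under treatment to that patient's own baseline, and it does not combine visits. If some patients clear while others turn positive, the two cancel in the table. A baseline-to-worst shift table exists to separate these movements.

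Some positive results at baseline are plausible. The trial admits diabetic patients with HbA1c up to 8% and excludes reduced renal function only below an eGFR of 30 ml/min (protocol 5.4). At stake is a clear count, for each dose, of patients whose urine result became abnormal under treatment. The protocol planned a table that gives it; the SAP's urine output does not, and no reason is offered.

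**Working it through.** The plan states no figure on this point, so there is nothing to reproduce. The check is a comparison of texts, followed by a small calculation of what the planned table can reveal.

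**Texts side by side**

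| Output | Protocol 10.1.4 | SAP 3.6.2 |
|---|---|---|
| Classification against ranges or classes | Biochemistry, haematology, urine | Biochemistry and haematology against ranges; urine in dipstick classes |
| Shift table, baseline to worst | Biochemistry, haematology, urine | Biochemistry and haematology only |
| Count of patients with an emergent abnormality | Not separately stated | Biochemistry and haematology only |
| Urine by visit | Value at the visit | Classes at baseline and each visit under treatment |

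The only laboratory rationale in SAP 3.6.2 is that local laboratories supply the results, so no quantitative analysis is done. The SAP does not offer this as a reason for treating urine differently. It would not serve as one: shift tables are kept for the local-laboratory parameters, and the dipstick is a qualitative test done at the site.

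**What marginal counts can show**

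Inputs: SAP 1.3 gives 121 included patients over six groups, and 121/6 = 20.2, so take N = 20. The positive counts below are assumed, because the documents give none.

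Let B be the number positive at baseline, P the number positive at a later visit, and x the number newly positive at that visit. The P positives are x new ones plus some of the B baseline positives. So:

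max(0, P − B) ≤ x ≤ min(P, N − B)

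- B = 4, P = 4: lower bound max(0, 0) = 0; upper bound min(4, 16) = 4. Between 0 and 4 of the 16 baseline negatives (0% to 25%) turned positive.
- B = 2, P = 3: lower bound max(0, 1) = 1; upper bound min(3, 18) = 3.

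Across the two visits on drug, W004 and W006, with B = 4 and P = 4 at each, the number newly positive at either visit lies between 0 (the same four patients throughout) and min(16, 4 + 4) = 8. A shift table gives the exact number.

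**Role of W008**

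W008 is left out of this calculation because dosing stops at W006. SAP 3.1.2 counts a value as under treatment up to 15 days after the last intake. Protocol 6.1 puts W008 at 14 ± 4 days after W006, that is 10 to 18 days. So W008 results count for some patients and not for others.

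**Which parameters are left uncovered**

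Protocol 8.2 measures total bilirubin and glucose in serum, along with creatinine, urea, albumin and total protein. All of these fall under the SAP's biochemistry shift tables. Urine blood, protein, leucocytes and nitrites are the main remainder.

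**The case against.** The strongest case on the other side is that little is lost.

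- **The data remain.** Dipstick results are held per patient, so the count can be produced at any time. This stands: only a pre-specified table is missing. A reader might infer that new positives cannot be counted by dose at all, but that is true of the planned tables and not of the data.
- **The tables are by group.** SAP 3.6 gives urine classes for each dose and for placebo. Suppose two of four baseline positives clear in each arm and two new positives appear on drug only. Placebo then falls to 2/20 while the drug arm stays at 4/20, and the difference shows. This stands for net change. A reader might infer that the urinalysis part of the safety objective goes unanswered by dose; it is answered in part, without within-patient change.
- **Other routes exist.** Clinically significant abnormal results should be recorded as adverse events (protocol 8.2 and 8.3.1.1) and counted by group. This helps, but it depends on the investigator's judgement of significance. SAP 3.6.2 also plans a listing of emergent out-of-range values. It follows the biochemistry and haematology bullets, and SAP 3.1.2 defines emergence by numerical limits that do not fit dipstick classes. Even if it covers urine, it is a listing and not a count.
- **Some adaptation was needed.** Reference ranges and alert values do not map directly to a dipstick grade. This explains using classes, but not dropping the shift table, which works well with ordered classes.
- **The change table claims main changes only, and the table templates are a separate document.** Both are fair. A urine shift table may exist in the templates, which are not available here; if so, the SAP text should say so.
- **No urinary signal is flagged.** Protocol section 2 reports less than 0.1% of radioactivity excreted in urine, and protocol 8.3.1.3 defines no events of special interest. This limits the importance of the point.

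**Conclusion.** The discrepancy is real and undeclared: protocol 10.1.4 includes urine in the baseline-to-worst shift tables and SAP 3.6.2 does not. The planned urine tables do not show how many patients per dose moved from negative at baseline to positive under treatment. In an arm of 20 with assumed counts of 4 positive before and 4 after, that number could be anywhere from 0 to 4 at one visit.

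Severity is minor. The point concerns one descriptive safety output, mainly for urine blood, protein, leucocytes and nitrites, and does not touch the primary analysis. A reader might infer that new bilirubin or glucose findings would go unseen; the serum shift tables largely cover those. Nor should the three post-baseline visits be pooled as if all were on drug, since W008 follows the end of dosing.

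The conclusion rests on the SAP text as it stands, without sight of the table templates or the Specifications document. The counts are illustrative; only the arm size comes from the documents.

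**What to change.** In SAP 3.6.2, add for each graded dipstick parameter, by treatment group:

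- a shift table from the baseline class to the worst class under treatment;
- the number and percentage of patients with an emergent positive result, with those negative at baseline as the denominator.

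State which class counts as positive and fix it before unblinding. Neither document gives a cut-off; one option is absent or trace at baseline and + or higher under treatment. Say how W008 results are handled under the 15-day rule. Summarise pH separately, because it does not fit classes running from absent upwards.

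If the sponsor prefers to keep the per-visit description alone, the departure from protocol 10.1.4 should be entered in the SAP's table of main changes with a reason.

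The cost is a few lines of SAP text and one more run of a table type already planned for biochemistry and haematology. No new data are needed, and sample size, power and type I error do not change.

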8.3. Adverse events

All adverse events and other situations relevant to the safety of the participants must be followed up and fully and precisely documented in order to ensure that the sponsor has the necessary information to continuously assess the benefit-risk balance of the clinical trial.

The same procedure applies whether the participant receives the test drug or a comparison product (placebo, S42909).

8.3.1. Definitions

8.3.1.1. Adverse events

An adverse event is defined as any untoward medical occurrence in a subject participating in a clinical study, whether or not there is a causal relationship with the IMP and/or experimental procedures, occurring or detected from the date the participant signs the information and consent form, irrespective of the period of the study (periods without administration of the IMP (e.g. selection period) are also concerned).

An adverse event can therefore be:

- any unfavourable and unintended sign, including an abnormal finding from an additional examination (lab tests, X-rays, ECG, etc.) which is deemed clinically relevant by the investigator,
- any symptom or disease,
- any worsening during the study of a symptom or a disease already present when the participant entered the study (increase in frequency and/or intensity), including the studied pathology,

and detected during a study visit or at an additional examination or occurred since the previous study visit (including relevant event reported in participant's diary or safety evaluation scale).

Of note:

- Any **hospitalisation for social reasons, educational purpose** (e.g. learning of arterial hypertension management by the participant) or routine check-up, and the hospitalization for PK sampling purposes at W004 (participants having signed the consent form for the optional PK analysis) should not be considered as an adverse event and should not be reported in the e-CRF.
- The following procedures, whether planned before the study or not, whether leading to a hospitalisation or not, should be reported in the specific page "**Procedures not subsequent to an adverse event**" of the e-CRF:

- therapeutic procedures related to a non-aggravated medical history (e.g. cataract extraction not due to an aggravation of the cataract during the study, haemodialysis sessions related to a renal insufficiency not aggravated during the study),
- prophylactic procedures (e.g. sterilisation, wisdom teeth removal),
- comfort procedures (e.g. cosmetic surgery),
- control procedures of a pre-existing condition without aggravation (e.g. colonoscopy to control the remission of colon cancer).
- any hospitalisation to perform the duplex ultrasonography examination

- In the framework of this protocol, local adverse reactions at ulcer site such as pruritus, erythema, pain, discomfort, bleeding, etc., are reactions that are expected to occur in normal conditions during the healing process and investigators should use their clinical judgement to discern whether a specific event is falling into this category or not. Expected local adverse reactions should not be reported as adverse events.

